## 3 ELIGIBILITY CRITERIA

### 3.1 Inclusion Criteria

#### Definitions:

- **Androgen Deprivation Therapy** includes LHRH agonist or LHRH antagonist or bilateral orchiectomy. Anti-androgen receptor blockers (e.g. bicalutamide) do not constitute androgen deprivation therapy.
- **Protocol specified therapy** refers to the androgen deprivation therapy (see above) with or without radium-223 dichloride.

1. All subjects or their legally authorized representative must be informed of the investigational nature of the study and provide written informed consent and HIPAA authorization for release of personal health information before performance of any study related procedure not part of routine medical care.  
**NOTE:** HIPAA authorization may be included in the informed consent or obtained separately.
2. Men  $\geq$  18 years of age at the time of informed consent.
3. Histological or cytological evidence of prostate adenocarcinoma.
4. All subjects must have radiologic or pathologic evidence of skeletal metastases with  $\geq$  2 skeletal lesions with or without pain at baseline on bone scan or axial imaging or with 1 skeletal lesion and bone pain within 28 days prior to the registration.
5. All subjects must have a radiographic assessment (chest or abdominal/pelvic CT or MRI) within 28 days prior to registration but do not need to have measurable disease.
6. ECOG (Eastern Cooperative Oncology Group) Performance Status of 0-2 within 28 days prior to registration (see Study Procedures Manual [SPM] for ECOG Performance Status definitions). ECOG Performance Status of 3 will only be allowed if judged by the site investigator as attributable exclusively to bone pain.
7. Subjects must fall into one of the two populations below:
  - **Early Induction Group:** Subjects who have started androgen deprivation therapy (luteinizing hormone–releasing hormone (LHRH) agonist or antagonist therapy with or without an antiandrogen agent) a maximum of 28 days before registration and who otherwise meet all the eligibility criteria.
  - **Late Induction Group:** Subjects who have NOT started any androgen deprivation therapy (luteinizing hormone–releasing hormone (LHRH) agonist or antagonist therapy with or without an antiandrogen agent).

8. Anti-androgen receptor antagonist therapy must be bicalutamide. Subjects already started on other anti-androgens must be willing to switch over to bicalutamide.

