#### 5.3 Androgen Receptor Antagonist

All subjects will receive bicalutamide. Subjects may start bicalutamide within 14 days prior to starting a LHRH agonist/antagonist or the date of bilateral orchiectomy at the discretion of the treating investigator to prevent a clinical flare reaction. Subjects on other anti-androgens prior to registration must switch to bicalutamide without lead-in.

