## 5.5 Designation of Cycle 1 Day 1 date

Cycle 1 Day 1 is designated as the day the subject receives LHRH agonist or antagonist (androgen deprivation therapy) or the date of bilateral orchiectomy. The early induction subjects will have already received their first LHRH agonist or antagonist injection or had bilateral orchiectomy. Please verify this date for early induction subjects with source documentation.

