- CT and MRI scans if clinically indicated can be performed with or without intravenous contrast as per institutional guidelines at screening, C8D1, C13D1 and C17D28 (a window of ± 7 days for all scans is allowed). DEXA scan will be performed at screening and after completion of 1 year of treatment. CT or Brain MRI: Brain imaging studies are not required for eligibility if the subject has no neurologic signs or symptoms suggestive of brain metastasis. Subjects

with neurological symptoms are recommended to undergo a head CT scan (with or without intravenous contrast) or brain MRI (with or without intravenous contrast) to exclude brain metastasis. If brain imaging studies are performed, they must be negative for CNS disease. Skull bone involvement without neurological impact by prostate cancer is allowed. A bone scan will be performed at baseline, C8D1 and after completion of 1 year of treatment.

9. All subjects will receive androgen deprivation therapy with a LHRH agonist (any LHRH agonist such as leuprolide acetate or goserelin acetate is acceptable) or a LHRH antagonist (degarelix) or bilateral orchiectomy per the treating physician. Androgen Deprivation therapy with LHRH agonist or LHRH antagonist will be given continuously.
10. MANDATORY: Serum submission for Bone Turnover Markers: Pre-Dose Cycle 1 Day 1 (late induction group) and thereafter on Day 1 of each cycle during the remaining 6 months of protocol specified therapy and at End of Treatment (both induction groups). CTCs: For following time points only: C1D1 (late induction group only); C2D1 (early induction group only); C4D1; EOT visit. CTCs will be collected for all subjects (n = 204). See Correlative Laboratory Manual (CLM) for collection, labeling and shipping instructions.
11. MANDATORY: Whole blood for banking is to be collected pre dose Cycle 1 Day 1 (late induction group) or pre dose Cycle 2 Day 1 (early induction group) and at EOT. Serum and plasma are to be collected at Pre-Treatment Cycle 1 Day 1 (late induction group) or Cycle 2 Day 1 (early induction group) and at EOT. See CLM for collection, labeling, processing and shipping instructions.

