### **9.3 Samples for future studies**

Subject consent will be obtained for additional samples collected for future studies. Hoosier Cancer Research Network will manage the banked samples. Samples will be banked indefinitely in the Hoosier Cancer Research Network biorepository.

This includes:

- Whole blood: Mandatory
  - Whole blood will be collected prior to treatment on Cycle 1 Day 1 (late induction group) or Cycle 2 Day 1 (early induction group).
- Pre- and Post-treatment plasma: Mandatory
  - Whole blood for plasma will be collected prior to treatment on Cycle 1 Day 1 (late induction group) or Cycle 2 Day 1 (early induction group) and at End of Treatment (both groups).
- Pre- and Post-treatment serum: Mandatory
  - Whole blood for serum will be collected prior to treatment on Cycle 1 Day 1 (late induction group) or Cycle 2 Day 1 (early induction group) and at End of Treatment (both groups).

Please refer to the CLM for all sample collection, processing, labeling and shipping instructions.

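### The late-induction Cycle 1 Day 1 baseline may be taken on bicalutamide, and the Section 12.7 split by ADT start would count those men as untreated

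*Combined protocol and SAP*

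**What the plan says.** Footnote 10 of the study calendar (Section 7) schedules bone-marker serum "Pre-Dose Cycle 1 Day 1 (late induction group) and thereafter on Day 1 of each cycle" of induction, and again at end of treatment. In the late-induction group, CTCs and banked blood (footnotes 10 and 11, Section 7.2) and the BPI and WHO scores (footnote 7, Section 9.5) are also first taken on Cycle 1 Day 1.

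That day is tied to castration therapy. Section 5.5 states: "Cycle 1 Day 1 is designated as the day the subject receives LHRH agonist or antagonist", or has a bilateral orchiectomy. Bicalutamide follows its own clock. Under Section 5.3, "All subjects will receive bicalutamide", and "Subjects may start bicalutamide within 14 days prior to starting a LHRH agonist/antagonist or the date of bilateral orchiectomy", at the investigator's discretion.

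The definitions in Section 3.1 add that "Anti-androgen receptor blockers (e.g. bicalutamide) do not constitute androgen deprivation therapy". The same list limits the protocol's own therapy to ADT, given alone or combined with radium-223, so bicalutamide lies outside that term too.

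In its correlative study design, Section 9.1 says that early-induction men will have no pre-treatment bone-marker specimen. Its specific aims use baseline and pre-treatment sera as equivalent terms when describing prognostic value. Section 12.7 plans to compare marker levels between men who had and had not started ADT before randomization. If prior ADT appears to matter, all marker analyses are to be stratified by ADT initiation status.

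**The concern.** The late-induction Cycle 1 Day 1 serum is the only bone-marker specimen that the plan regards as untreated, and the hypothesis that baseline markers are prognostic in newly diagnosed disease depends on such specimens. If some of those men are already on an androgen-receptor blocker, the late-induction baseline mixes untreated men with men exposed for up to two weeks.

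Two analyses are exposed. Change from baseline in markers and pain would start from a treated value in some men. The ADT comparison in 12.7, the only planned check on this kind of contamination, would place bicalutamide-exposed men in its untreated reference group. An untreated sample that is not drawn cannot be obtained later.

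**Working it through.** No sample size, event count, power or alpha is in question, so there is no planned figure to reproduce. The check sets the sections side by side and then makes one exposure calculation.

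**Can a late-induction man be on bicalutamide at his baseline sample?**

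1. Late induction means that no ADT has been started (3.1, item 7). Antiandrogens are not ADT (3.1, Definitions), so a man on bicalutamide alone is still late induction. Item 8 of 3.1 and Section 5.3 both foresee antiandrogen use before registration.
2. Cycle 1 Day 1 is the LHRH or orchiectomy date (5.5), and bicalutamide may precede it by 0 to 14 days (5.3). The calendar shows both drugs starting on Cycle 1 Day 1 and so does not display the lead-in.
3. Pre-dose on Cycle 1 Day 1 (footnote 10, Section 7.2) is satisfied by a draw before the LHRH injection. No text in the protocol requires the draw to precede the first bicalutamide tablet.

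The answer is yes, it can happen. How often is not stated.

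**Does the 12.7 check catch it?**

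4. The split is by whether ADT was started before randomization. By the 3.1 definition, a bicalutamide lead-in leaves a man in the not-started group.
5. Section 4 requires therapy to begin within 5 business days of randomization. If therapy there means protocol specified therapy as defined in 3.1, a lead-in begun after randomization lasts about a week at most, and one of 14 days must have begun before randomization. A long lead-in is therefore misclassified because antiandrogens are not counted. A short one begun between randomization and Cycle 1 Day 1 would also be missed because the split is anchored to randomization and not to the sample.

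**How much drug could be on board?**

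Inputs are the lead-in d, from 0 to 14 days (5.3), and the elimination half-life h, from 7 to 10 days (10.2). Assuming first-order accumulation on daily dosing, the fraction of steady state is f = 1 − 2^(−d/h).

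| Lead-in d | h = 7 days | h = 10 days |
|---|---|---|
| 0 days | 0 | 0 |
| 3 days | 0.257 | 0.188 |
| 7 days | 0.500 | 0.384 |
| 14 days | 0.750 | 0.621 |

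The longest permitted lead-in thus reaches about 62% to 75% of steady state. This describes drug level only. The documents do not report how bicalutamide alone moves bone markers, CTCs or pain over two weeks.

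**The case against.** **The wording is consistent if pre-dose means pre-LHRH.** This stands as a reading of footnote 10, since bicalutamide is neither ADT nor protocol specified therapy. It does not rescue 9.1, which treats the sample as pre-treatment, or 12.7, which treats the man as not yet exposed.

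**Sections 9.3 and 9.5 do not promise an untreated baseline.** A reader might infer that they do, because they speak of samples taken before treatment and of a pre-treatment WHO score. Both sections pair Cycle 1 Day 1 with Cycle 2 Day 1 in early-induction men, who by then have had about 28 days of ADT. The phrase there can only mean before that visit's dose, and the BPI is not called pre-treatment at all. This stands, and the point rests on 9.1 and 12.7.

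**PSA and ALP need not be affected.** Section 7.1 allows both to be drawn at screening, and Section 7.2 then waives the repeat. They may precede any lead-in, though this is not guaranteed. The 7-month PSA endpoints are absolute values, so baseline PSA does not enter them.

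**The consequences are limited.** The bone-marker assays await funding (9.1), the correlative work is declared exploratory, and the models may be expanded with other subject factors (12.7). The plan already accepts early-induction men with no pre-ADT marker. All of this stands and keeps the point minor.

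**Existing procedures may cover part of it.** Concomitant medications are reviewed at screening and Cycle 1 Day 1, so a start date may already be captured. No planned analysis uses it. Detailed collection instructions are in the Correlative Laboratory Manual, which is not among the documents available here.

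**Conclusion.** The point holds as a minor improvement. Some late-induction baseline markers, CTCs and pain scores may be taken on bicalutamide, after at most 14 days of exposure under 5.3, and 12.7 would count those men as untreated.

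Three stronger readings are tempting but not supported:

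- **That part of the baseline is on drug.** The lead-in is optional and the share is not given. It could be anywhere from 0 to 100% of late-induction men.
- **That the loss can be quantified.** Assume that 25% to 50% of late-induction men have a lead-in (p) and that it shifts a marker by 0.25 to 1 SD (d). The added baseline variance p(1 − p)d² runs from 0.25 × 0.75 × 0.0625 = 0.012 to 0.5 × 0.5 × 1 = 0.25. The marker-outcome correlation is then multiplied by 1/√(1 + added variance), or 0.994 to 0.894. Both inputs are assumptions, the result applies to the late-induction subgroup only, and even the direction of a shift is unknown. The range is an illustration and cannot serve as an estimate.
- **That the treatment comparison is biased.** Bicalutamide and its lead-in rule are common to both arms, so no between-arm bias is expected. The baseline samples play no part in rPFS.

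The point is therefore confined to the exploratory prognostic-marker and change-from-baseline analyses.

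**What to change.** 1. Record the date of the first antiandrogen dose as its own data field.
2. In 12.7, define prior treatment as any antiandrogen, LHRH therapy or orchiectomy before the baseline sample. Use that definition, in place of ADT started before randomization, for the marker comparison and any resulting stratification.
3. In footnotes 7, 10 and 11 and in Section 7.2, have the late-induction baseline sample and questionnaires collected before the first dose of any hormonal agent where this is possible after consent. Otherwise flag the sample as taken on antiandrogen. Men who began an antiandrogen before consent cannot give an untreated sample, and for them the date field and the 12.7 definition do the work.

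The cost is wording, one date field, and the same draw and questionnaires up to 14 days earlier in men with a lead-in. For those men the draw may not fall on the LHRH visit day. The lead-in and the treatment schedule are unchanged.

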### 7.1 Screening within 28 days prior to registration for protocol therapy

- Informed Consent
- Medical history including diagnosis and staging information. For **early** induction subjects, note details of ADT therapy initiation during medical history. This review should also include laboratory values and radiology imaging completed prior to and during ADT.
- Physical examination and history of secondary malignancies. Close monitoring for fractures should be done during all physical exams. If a fracture is suspected radiological exams should be performed per clinical guidelines. Subjects should be encouraged to contact the site investigator for any new onset pain or increase in pain in sites of known bone disease.
- Vital signs including BP measurement, height (screening only) and weight, and ECOG performance status.
- Assessment of adverse events and concomitant medications
- Laboratory Testing:
  - Comprehensive metabolic panel (sodium, potassium, chloride, bicarbonate, blood urea nitrogen (BUN), serum creatinine, glucose, calcium, total protein, albumin, AST, ALT, alkaline phosphatase, total bilirubin), magnesium, phosphorus,
  - CBC (WBC with differential and platelet count, hemoglobin and hematocrit)
  - Testosterone; Late induction subjects; may be done during screening or prior to C1D1 treatment for. Early induction subjects; if available, an alkaline phosphatase prior to initiation of ADT should be obtained through medical record review or prior to treatment C2D1.
  - Alkaline phosphatase; Late induction subjects; may be done during screening or prior to C1D1 treatment for. Early induction subjects; if available, an alkaline phosphatase prior to initiation of ADT should be obtained through medical record review or prior to treatment C2D1.
  - PSA; Late induction subjects; may be done during screening or prior to C1D1 treatment for. Early induction subjects; if available, an alkaline phosphatase prior to initiation of ADT should be obtained through medical record review or prior to treatment C2D1.
- Imaging:
  - CT or MRI abdomen/pelvis,
  - DEXA scan
  - Bone Scan
  - CT or MRI Brain, Chest X-Ray or Chest CT if clinically indicated. See eligibility criteria.

**NOTE: Subjects that have NOT received any ADT prior to screening are considered “Late Induction” and subjects that have initiated ADT prior to screening are considered “Early Induction.”**

## 7.2 Induction: Cycle 1 Day 1

**NOTE:** Cycle 1 Day 1 lab testing need not be repeated if completed within 7 days of starting protocol therapy. C1D1 is retrospective for early induction group and verified during Medical History with review of medical records.

- Physical examination. Close monitoring for fractures should be done during all physical exams. If a fracture is suspected radiological exams should be performed per clinical guidelines. Subjects should be encouraged to contact the site investigator for any new onset pain or increase in pain in sites of known bone disease.
- Vital signs including BP measurement, weight, ECOG performance status
- Assessment of adverse events and concomitant medications
- Laboratory Testing:
  - CMP to include sodium, potassium, chloride, bicarbonate, blood urea nitrogen (BUN), serum creatinine, glucose, calcium, total protein, albumin, AST, ALT, alkaline phosphatase, total bilirubin. Including magnesium, phosphorus
  - CBC (WBC with differential and platelet count, hemoglobin and hematocrit) Additional monitoring of CBC w/diff and platelet per site investigator's discretion based on subject clinical status.
  - Serum testosterone; late induction subjects. If done at screening, no need to repeat
  - Alkaline phosphatase; late induction subjects. If done at screening, no need to repeat
  - PSA; late induction subjects. If done at screening, no need to repeat
- Correlative Studies for late induction group:
  - Serum bone turnover markers collected pre-dose
  - Circulating tumor cell's (CTCs) collected pre-dose
  - Banking Samples (pre-dose): whole blood, serum, plasma
- Surveys: pain assessment with BPI (short form) and WHO ladder

## 7.3 Induction: Cycle 2 - Cycle 7 Day 1 ( $\pm 7$ days)

- Physical examination. Close monitoring for fractures should be done during all physical exams. If a fracture is suspected radiological exams should be performed per clinical guidelines. Subjects should be encouraged to contact the site investigator for any new onset pain or increase in pain in sites of known bone disease.
- Vital signs including BP measurement, weight, ECOG performance status
- Assessment of adverse events and concomitant medications.
- Laboratory Testing:
  - CMP to include sodium, potassium, chloride, bicarbonate, blood urea nitrogen (BUN), serum creatinine, glucose, calcium, total protein, albumin, AST, ALT, alkaline phosphatase, total bilirubin. Including magnesium, phosphorus
  - CBC (WBC with differential and platelet count, hemoglobin and hematocrit) Additional monitoring of CBC w/diff and platelet per site investigator's discretion based on subject clinical status
  - Serum testosterone
  - Alkaline phosphatase
  - PSA
- Correlative Studies:
  - Serum bone turnover markers collected pre-dose

**EARLY INDUCTION ONLY Cycle 2 Day 1 (In addition to the testing listed above)**

- Alkaline phosphatase
- PSA
- Correlative Studies:
  - Circulating tumor cell's (CTCs): collected pre-dose
  - Banking Samples: whole blood, serum, plasma collected pre-dose
- Surveys: pain assessment with BPI (short form) and WHO ladder.

**7.4 Cycle 4 Day 1 (in addition to testing listed above)**

- Correlative Studies:
  - Circulating tumor cell's (CTCs): collected
- Surveys: pain assessment with BPI (short form) and WHO ladder.

**7.5 Post Induction Cycle 8 Day 1 ( $\pm$  7 days)**

- Physical examination. Close monitoring for fractures should be done during all physical exams. If a fracture is suspected radiological exams should be performed per clinical guidelines. Subjects should be encouraged to contact the site investigator for any new onset pain or increase in pain in sites of known bone disease.
- Vital signs including BP measurement, weight, ECOG performance status
- Assessment of adverse events and concomitant medications.
- Laboratory Testing:
  - CMP to include sodium, potassium, chloride, bicarbonate, blood urea nitrogen (BUN), serum creatinine, glucose, calcium, total protein, albumin, AST, ALT, alkaline phosphatase, total bilirubin. Including magnesium, phosphorus
  - CBC (WBC with differential and platelet count, hemoglobin and hematocrit) Additional monitoring of CBC w/diff and platelet per site investigator's discretion based on subject clinical status
  - Testosterone
  - Alkaline phosphatase
  - PSA
- Surveys: pain assessment with BPI (short form) and WHO ladder.
- Imaging:
  - CT or MRI abdomen/pelvis
  - Bone Scan
  - Chest x-ray or Chest CT if clinically indicated

**7.6 Post Induction Cycles 9-12 ( $\pm$  7 days)**

**NOTE:** ADT may continue for up to 2 years from randomization

- Laboratory tests D1 of each cycle:
  - PSA
  - Alkaline phosphatase
- Assessment of adverse events and concomitant medications. This may be done via email, phone call or medical record review

### 7.7 Maintenance: Cycle 13 Day 1; 12 months from ADT initiation ( $\pm 7$ days):

- Clinical: Physical examination including BP measurement, weight, ECOG performance status, assessment of adverse events and concomitant medications. Close monitoring for fractures should be done during all physical exams. If a fracture is suspected radiological exams should be performed per clinical guidelines. Subjects should be encouraged to contact the site investigator for any new onset pain or increase in pain in sites of known bone disease.
- Laboratory Testing:
  - CMP to include sodium, potassium, chloride, bicarbonate, blood urea nitrogen (BUN), serum creatinine, glucose, calcium, total protein, albumin, AST, ALT, alkaline phosphatase, total bilirubin, magnesium, phosphorus
  - CBC (WBC with differential and platelet count, hemoglobin and hematocrit)
  - Serum testosterone
  - Alkaline phosphatase
  - PSA
- Imaging:
  - CT or MRI abdomen/pelvis
  - DEXA scan
  - Bone Scan
  - Chest x-ray or Chest CT if clinically indicated

### 7.8 Maintenance Cycles 14-16 Day 1 ( $\pm 14$ days)

**NOTE:** ADT may continue for up to 2 years from randomization. Maintenance Cycles will = 84 days/12 weeks.

- Laboratory tests:
  - PSA
  - Alkaline phosphatase
- Assessment of adverse events and concomitant medications. This may be done via email, phone call or medical record review

### 7.9 Maintenance Cycle 17 Day 28

- Physical examination. Close monitoring for fractures should be done during all physical exams. If a fracture is suspected radiological exams should be performed per clinical guidelines. Subjects should be encouraged to contact the site investigator for any new onset pain or increase in pain in sites of known bone disease.
- Vital signs including BP measurement, weight, ECOG performance status
- Assessment of adverse events and concomitant medications.
- Laboratory Testing:
  - CMP to include sodium, potassium, chloride, bicarbonate, blood urea nitrogen (BUN), serum creatinine, glucose, calcium, total protein, albumin, AST, ALT, alkaline phosphatase, total bilirubin. Including magnesium, phosphorus
  - CBC (WBC with differential and platelet count, hemoglobin and hematocrit)  
Additional monitoring of CBC w/diff and platelet per site investigator's discretion based on subject clinical status
  - Alkaline phosphatase
  - PSA

- Imaging:
  - CT or MRI abdomen/pelvis
  - Chest x-ray or Chest CT if clinically indicated

